5.3.4 Patient Satisfaction

At the 12 and 24 month follow-up visits, subjects will be asked whether they were happy with the outcome of their surgery (Yes/No) and whether they would repeat the operation (Yes/No).

5.3.5 Odom's Criteria Patient Satisfaction

At the 24 month follow-up visit, the Investigator will rate the clinical disposition of each study subject according to Odom's Criteria as follows:

Excellent: all pre-operative symptoms relieved, able to carry out daily occupations without impairment.

Good: minimum persistence of pre-operative symptoms, able to carry out daily occupations without significant interference.

Fair/Satisfactory: relief of some pre-operative symptoms but physical activity is significantly limited.

Poor: symptoms or signs unchanged or worsened.

5.3.6 Surgery Time

The length of the surgical procedure from the initial incision to final closure will be captured from the Anesthesia Record.

5.3.7 Anesthesia Time

The length of time the patient is under anesthesia will be captured from the Anesthesia Record.

5.3.8 *Estimated Blood Loss*

The amount of blood loss over the entire length of the surgery, documented on the Anesthesia Record, will be captured.

5.3.9 *Length of Hospital Stay*

The length of hospital stay from the date of admission to the date of discharge will be calculated.

5.3.10 *Return to Work/School*

The ability to and the time it takes for the subject *to be cleared* to return to work/school from the date of surgery will be documented.

5.3.11 *Use of Narcotics Post-Surgery*

The types and dosages of any narcotics taken by the patient post-surgery will be documented.

6 STUDY ENDPOINT

The endpoint of this study is to determine that the restoration and/or maintenance of thoracic kyphosis and coronal curve correction is better than with similar CoCr systems.

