5 STUDY OBJECTIVES/OUTCOMES

5.1 Primary Effectiveness Objective

The primary effectiveness objective is:

Restoration and maintenance of thoracic kyphosis and coronal curve correction.

- Quantitative assessment:
 - Cobb Angles – Coronal and Sagittal
 - Thoracic kyphosis as measured from the upper endplate of T4 to the lower endplate of T12
 - Lumbar lordosis as measured from the lower endplate of L1 to the upper endplate of S1

The increased stiffness of the MESA Rail is designed for the restoration and maintenance of thoracic kyphosis as well as coronal correction of deformities such as AIS after surgery. The restoration and subsequent maintenance of the thoracic kyphosis and coronal curve correction during surgery is expected to be as good as if not better than results reported for standard Ø5.5mm and Ø4.5mm CoCr pedicle screw and rod systems in these patient populations.

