12.2 Study Hypothesis

The primary objective of this study is to evaluate the effectiveness of the MESA Rail Deformity System in terms of restoring and maintaining thoracic kyphosis in the treatment of patients with symptomatic AIS. The primary effectiveness endpoint is the rate of overall subject success (minimal loss of thoracic kyphosis) at 24 months. The primary hypothesis of this trial is that the clinical performance of the K2M MESA Rail implant is non-inferior to the clinical performance achieved and achieved with fusion utilizing a standard Ø5.5mm or Ø4.5mm CoCr rod.

A PubMed literature review was conducted to assemble relevant publications utilizing results from posterior instrumentation fusion surgeries in patients with AIS. Searches included all peer-reviewed journals published between January 2000 and March 2013. Sample sizes, patient populations, evaluated variables, results, and recorded complications were assessed for each selected article. Only data regarding thoracic kyphosis measurements of single-stage posterior fusion cases were incorporated into the thoracic kyphosis table used for statistical analysis. Articles were entirely excluded from the statistical analysis if results combined data from multi-stage cases or if data were extracted through meta-analysis.

The following table gives the preoperative thoracic kyphosis measurements as well as the thoracic kyphosis measurements collected at the last follow-up period from all relevant posterior fusion surgeries in patients with AIS:

| Thoracic Kyphosis | | | | | | | | | |
|----------------------------------|-----|-------|------|---------|------|------|------|---------------------|-------------|
| paper # | n | Preop | | Last FU | | Diff | | Mean difference x N | Std Dev x N |
| | | Mean | SD | Mean | SD | Mean | SD | | |
| 1 ¹ | 9 | 31.9 | 10.4 | 26.0 | 9.8 | 5.9 | 10.1 | 53.1 | 90.9 |
| 1 | 3 | 31.0 | 9.5 | 29.7 | 5.5 | 1.3 | 7.5 | 3.9 | 22.5 |
| 1 | 34 | 28.2 | 13.0 | 26.5 | 11.0 | 1.7 | 12.0 | 57.8 | 408.0 |
| 1 | 9 | 23.0 | 8.0 | 23.0 | 11.0 | 0.0 | 9.5 | 0.0 | 85.5 |
| 1 | 60 | 26.7 | 13.0 | 25.0 | 9.6 | 1.7 | 11.3 | 102.0 | 678.0 |
| 1 | 31 | 22.8 | 11.0 | 25.7 | 8.8 | -2.9 | 9.9 | -89.9 | 306.9 |
| 2 ² | 83 | 23.0 | 12.0 | 20.2 | 8.4 | 2.8 | 11.4 | 234.9 | 946.2 |
| 3 ³ | 111 | 29.0 | 14.0 | 23.0 | 10.8 | 6.0 | 12.2 | 666.0 | 1354.2 |
| 3 | 299 | 22.0 | 14.1 | 22.0 | 10.3 | 1.0 | 5.0 | 299.0 | 1495.0 |
| Weighted Mean Difference and SD: | | | | | | | | 2.1 | 8.4 |

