The study hypothesis is that the RAIL system is superior to other systems in Thoracic Kyphosis Correction. The hypotheses can be written:

$$\begin{aligned} H_0: \mu_R &< OPC - \delta \\ H_1: \mu_R &\geq OPC - \delta \end{aligned}$$

where μ_R is the mean Thoracic Kyphosis Correction of the RAIL system and OPC is the Objective Performance Criteria of 2.2 and $\delta = 2$ degrees.

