12.3 Sample Size

If the mean Thoracic Kyphosis Correction of the RAIL system is 4.0 with a standard deviation of 8.4, then 173 subjects provides 80% power to detect a statistically significant difference between the mean correction and the OPC of 2.2 using a two-sided one-sample t-test at a significance level of 0.05. In order to account for approximately 15% attrition, based on clinical experience, 204 subjects will be enrolled.

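### Section 6 states the study endpoint as restoration and/or maintenance being better than CoCr, which conflicts with Section 5.1 and with the single kyphosis test in Section 12, and the protocol does not say which governs

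*Combined protocol and SAP*

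**What the plan says.** Section 6 (Study Endpoint) is one sentence. The aim is to determine that "restoration and/or maintenance of thoracic kyphosis and coronal curve correction is better than with similar CoCr systems". It names no visit, statistic, comparator value or significance level.

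The other sections differ:

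- **Section 5.1** gives the primary effectiveness objective as "Restoration and maintenance of thoracic kyphosis and coronal curve correction", with and in place of and/or. The synopsis and Section 4.1 do the same. Section 5.1 also lists coronal and sagittal Cobb angles, T4-T12 kyphosis and "Lumbar lordosis as measured from the lower endplate of L1 to the upper endplate of S1" under that objective, without ranking them.
- **Section 12.2** narrows to kyphosis: "The primary effectiveness endpoint is the rate of overall subject success (minimal loss of thoracic kyphosis) at 24 months". It then gives two hypotheses. In one the device "is non-inferior to the clinical performance achieved" with CoCr rods; the other reads "The study hypothesis is that the RAIL system is superior to other systems in Thoracic Kyphosis Correction". The comparator is the "Objective Performance Criteria of 2.2", in degrees.
- **Section 12.3** sizes one comparison of a mean with that value, "using a two-sided one-sample t-test at a significance level of 0.05".
- **Section 12.5** plans one primary test, of thoracic correction against 2.2 degrees. It calls this an exact test of a success rate and gives no time point.

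No section states an order of precedence, a testing hierarchy, an alpha split or a rule that all components must succeed.

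**The concern.** Restoration (pre-op to initial post-op) and maintenance (initial post-op to 24 months) are different quantities. Both can be computed, because Section 8.4.1 schedules AP and lateral films at initial post-op, 6, 12 and 24 months. They can also move in opposite directions. As a purely hypothetical case, suppose the device gained 3 degrees more than the comparator at surgery and lost 4 degrees more afterwards. The net difference at 24 months is 3 - 4 = -1 degree, worse than the comparator, yet the restoration half of Section 6 would be met.

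At stake is what the final report may call success. If either half suffices, there are two chances at a favourable kyphosis result, while Section 12.3 budgets alpha for one test. Section 12 does not fully close the gap. Section 12.2 describes the endpoint in terms of loss, which is closer to maintenance; the hypotheses, 12.3 and 12.5 speak of correction, which is closer to restoration. Either reading could therefore cite a section in support.

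**Working it through.** **1. The plan's own sample size.** Inputs from Section 12.3: assumed mean 4.0, OPC 2.2, SD 8.4, two-sided alpha 0.05, power 80%, attrition about 15%.

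- Difference: 4.0 - 2.2 = 1.8. Standardised effect: 1.8 / 8.4 = 0.214.
- Noncentrality at n = 173: 0.214 × √173 = 2.82.
- Power of the one-sample t-test (noncentral t): 0.798 at n = 172 and 0.800 at n = 173, so n = 173.
- Enrolment: 173 / (1 - 0.15) = 203.5, rounded up to 204.

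Both figures reproduce. They belong to one kyphosis contrast tested once.

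**2. Error rate if either kyphosis contrast suffices.** Section 6 requires a better result, so only favourable rejections count: 0.05 / 2 = 0.025 per contrast. With both nulls true, standard normal test statistics Z1 and Z2, and correlation ρ:

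P(at least one favourable) = 0.025 + 0.025 - P(Z1 > 1.96 and Z2 > 1.96)

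The documents give no correlation, so ρ is assumed over a range.

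| ρ (assumed) | P(both) | P(at least one) | Ratio to 0.025 |
|---|---|---|---|
| -0.5 | <0.0001 | 0.050 | 2.0 |
| 0 | 0.0006 | 0.049 | 2.0 |
| 0.5 | 0.0046 | 0.045 | 1.8 |
| 0.8 | 0.0110 | 0.039 | 1.6 |

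**3. Error rate if coronal correction must also be better.** In the Section 6 sentence the *or* joins restoration and maintenance only; kyphosis and coronal correction are joined by *and*. The literal rule is then (kyphosis and coronal restoration both better) or (kyphosis and coronal maintenance both better). Simulating four equicorrelated normal statistics with all nulls true gives favourable-direction rates of 0.001 (ρ = 0), 0.009 (ρ = 0.5) and 0.017 (ρ = 0.8), all below 0.025. The rate rises towards the two-contrast value of 0.049 only if coronal correction is truly better and kyphosis is not.

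**4. Under Section 12.5 alone.** One two-sided test at 0.05 leaves the favourable-direction rate at 0.025.

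**5. Cost of keeping both alternatives.** With Bonferroni at 0.05 / 2 = 0.025 two-sided per contrast, and the 12.3 effect and SD assumed for both, 80% power needs 210 evaluable subjects, and 210 / 0.85 = 247.1, so 248 enrolled. At 173 evaluable, power per contrast falls to 0.711.

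**The case against.** The strongest reply is that Section 6 is not an operative decision rule. It has no test, alpha, threshold or time point, whereas Section 12 singles out kyphosis, gives one OPC, sizes one comparison and plans one primary test. The extra contrasts could not be run as the plan stands: the literature table in 12.2 holds only pre-op and last follow-up kyphosis, so there is no comparator value for restoration, for maintenance or for coronal correction. Section 12.7 plans only summaries and graphs for other variables.

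Much of this stands. It means the inflation is conditional on Section 6 being used as the rule and on benchmarks being chosen later. It does not remove the conflict, because no section says that Section 12 overrides the section titled Study Endpoint, and Section 12 is itself divided between rate and mean and between non-inferior and superior.

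A reader might infer that four alternatives are open (restoration or maintenance, kyphosis or coronal), with a correspondingly larger error rate. The grammar of the sentence does not support that, and there is no coronal benchmark to test against. A reader might also quote a family-wise rate that counts rejections in either direction; Section 6 requires a better result, so unfavourable rejections do not meet it.

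**Conclusion.** The point holds as an inconsistency that leaves the success rule open. Section 6 disagrees with the synopsis and Sections 4.1 and 5.1 on and versus and/or, and with Section 12 on what is tested and when. Taken at its word, it permits a claim of better results on restoration or maintenance alone that the one sized test would not support.

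If the two kyphosis contrasts were each tested at two-sided 0.05 and either sufficed, the favourable-direction error would be about 1.6 to 2 times the nominal 0.025. That rests on assumed correlations and on comparator values the documents do not supply. It would be wrong to conclude that the plan as written runs at an inflated error rate: under the 12.5 test it does not, and under the literal Section 6 sentence with the coronal condition and all nulls true the rate is below nominal. The wording should be settled before analysis.

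**What to change.** Replace the Section 6 sentence with one primary contrast: the mean change in T4-T12 thoracic kyphosis from pre-op to 24 months against the OPC, tested once with the two-sided 0.05 one-sample t-test of Section 12.3. State that only this result supports the primary conclusion. Define the sign of the change explicitly, because the 12.2 table computes pre-op minus last follow-up (for example 31.9 - 26.0 = 5.9), so a positive value there is a fall in kyphosis.

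Align the other sections:

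- **5.1:** name this contrast as primary, and move coronal correction and lumbar lordosis to secondary.
- **12.2:** choose a mean or a success rate, and superiority or non-inferiority. The sizing in 12.3 is for a mean tested for a difference from 2.2.
- **12.5:** replace the exact test of a success rate with the 12.3 test, and state 24 months.

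Report restoration, maintenance, coronal correction and lumbar lordosis as secondary estimates with 95% confidence intervals.

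The cost is wording only. No new data or patients are needed, and 173 evaluable and 204 enrolled stand. The downside for the sponsor is that success can no longer be claimed on restoration or maintenance alone.

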7 STUDY POPULATION

7.1 Sample Size

Two-hundred four (204) total subjects with the MESA Rail Deformity System at up to 18 clinical sites, geographically distributed worldwide.

7.2 Inclusion and Exclusion Criteria

To be eligible to participate in the study, a subject must meet all of the Inclusion Criteria and none of the Exclusion Criteria.

Inclusion Criteria

1. Diagnosis of AIS requiring surgical treatment for selective thoracic/lumbar fusion with a minimum of five (5) instrumented vertebrae between T1-S1 as confirmed by patient history and radiographic studies. AIS cases must be classified as a Lenke type 1 or type 2 curve. No cervical vertebrae are to be incorporated into the construct.
2. Willingness and ability to comply with the requirements of the protocol including follow-up requirements.
3. Willing and able to sign a study specific informed consent form or, in the case of a patient who is a minor, provide assent and the minor patient's parent/legal guardian provides written consent to participate.
4. Age range of ≥ 11 years old and ≤ 21 years old at time of surgery.

Exclusion Criteria

1. Previous anterior or posterior spine surgery at the index levels.
2. Previous posterior spine surgery (e.g., posterior element decompression) that destabilizes the cervical/thoracic/lumbar spine.
3. Active systemic infection or infection at the operative site.
4. Co-morbid medical conditions of the spine or upper/lower extremities that may affect the thoracic or lumbar spine neurological and/or pain assessment.
5. Metabolic bone disease such as osteoporosis that contradicts spinal surgery.
6. History of an osteoporotic fracture.
7. History of an endocrine or metabolic disorder (e.g., Paget's disease) known to affect bone and mineral metabolism.
8. Taking medications that may interfere with bony/soft tissue healing including chronic steroid use.
9. Known allergy to titanium or cobalt chrome.
10. Rheumatoid arthritis or other autoimmune disease or a systemic disorder such as HIV, active hepatitis B or C or fibromyalgia.
11. Insulin-dependent type 1 or type 2 diabetes.
12. Medical condition (e.g., unstable cardiac disease, cancer) that may result in patient death or have an effect on outcomes prior to study completion.
13. Pregnant, or intend to become pregnant, during the course of the study.
14. Severe obesity (Body Mass Index > 40).
15. Physical or mental condition (e.g., psychiatric disorder, senile dementia, Alzheimer's disease, alcohol or drug addiction) that would interfere with patient self-assessment of function, pain or quality of life.

16. Incarcerated at the time of study enrollment.
17. Current participation in an investigational study that may impact study outcomes.

7.3 Study Duration

Study subjects will be expected to participate in this study for 24 months following surgery, with follow-up evaluations at initial post-op, 3 months, 6 months, 12 months, and 24 months.

8 STUDY ENROLLMENT/EVALUATIONS

8.1 Patient Screening and Enrollment

Consecutive patients who potentially meet the study inclusion and exclusion criteria will be screened for eligibility. Diagnostic imaging studies to confirm the diagnosis of AIS with a Lenke type 1 or type 2 curve must be completed within 90 days of the planned date of surgery. If, at an interim point following the initial imaging, and prior to surgery, the subject experiences a significant change in his/her clinical presentation, the changes should be documented and the images repeated. Patients will be screened as follows:

- Consecutive patients are potentially eligible for entry into the study based on their age and whether their medical condition appears to generally fit the characteristics specific to this study.
- After the study is explained and questions are answered to the satisfaction of the prospective study participant, the patient being invited to participate in the study indicates their consent by signing the consent form (or a separate assent form, if required by your IRB/EC.) Any patient under the age of 18 being invited to participate in the study indicates their verbal assent, and their parent/guardian signs the consent form.
- *If required by your institution and/or IRB/EC:* If the child reaches the age of majority during the course of the study, consent to continue (re-consent) must be obtained using the current, approved consent form prior to any further study-specific procedures or assessments.
- A patient is considered enrolled in the study after signing the IRB/EC approved informed consent. Consented patients complete the remainder of the screening process to confirm study eligibility. Patients who do not fulfill the screening criteria are considered Screening Failures and will be documented on the Screening & Enrollment Log. Screening failures will not count against the total number of subjects eligible for analysis.
- Subjects who have signed (or had a parent/guardian sign) the informed consent and fulfilled the Inclusion/Exclusion criteria are then scheduled for surgery. It is important that surgery be scheduled within 90 days from the dates of the required pre-operative x-rays and within 90 days from the date that the subject completed the required pre-operative questionnaires for the study.

Once a patient is enrolled into the study, they will need to be given a unique subject identifying number (Subject ID) that will be used to capture de-identified information. For this study, the following standardized format will be used: *Site Identifying Number (2 digits)-Subject Identifying Number (3 digits)*. Your site identifying number will be assigned by the Sponsor, and the subject identifying number should start with 001 and continue accordingly during patient enrollment. For example, if the site identifying number issued to you is Site 03, and you are enrolling your second patient into the study, their Subject ID would be 03-002. A Patient Information Log will be provided to you to keep as a cross reference for study subjects.

8.2 Pre-Operative Evaluation

All subjects will complete the VAS and SRS-22r questionnaires within 90 days prior to the scheduled surgery. All patient questionnaires should be completed during the visit, preferably prior to the patient interacting with the Investigator or other clinical staff. A pertinent medical history will be documented and all subjects will undergo a standard neurological examination including assessments of sensation, motor function, and reflexes.

8.2.1 Pre-Operative Assessment

- Informed Consent/Assent
- Inclusion/Exclusion Criteria
- Demographics
- Pertinent History and Physical: Current Symptoms, Height, Weight and Tobacco Use
- Work/School Status

- Current Medication for Spine Problem
- Neurological Examination
- AP and Lateral X-rays
- Right and Left Lateral Bending X-rays (Pre-Operative Only)
- Back and Leg VAS and SRS-22r

8.3 Hospitalization/Surgery/Discharge

Subjects will be admitted to the hospital according to the Investigator's standard for non-cervical spine surgery. Prophylactic antibiotics may be administered prior to surgery in accordance with the surgeon's standard of care and anesthesia will be administered per standard operating procedures. The system will be implanted in accordance with methods detailed in the instructions for use for the MESA Rail Deformity System.

Data points required on the Operative case report form must be documented at the time of surgery. Intra-operative adverse events must be recorded and documented on an Adverse Event case report form.

A Subject may be excluded from the study intra-operatively at the discretion of the Investigator if unexpected findings/occurrences dictate deviation from the intended study procedure. Justification for an intra-operative exclusion and alternative surgical procedure must be fully documented in the subject's medical record and on the Study Exit case report form. A subject who is excluded intra-operatively will be considered an overall treatment failure.

If the patient experienced an adverse event(s) during the hospitalization it should be documented and recorded on an Adverse Event case report form. The subject may be instructed to return to normal activity at the discretion of the Investigator.

Additional post-operative restrictions may be imposed according to the standard of care normally utilized by the Investigator. In addition, subjects should be instructed to notify the Investigator if experiencing untoward events including but not limited to noticeable pain, numbness, tingling, or weakness that does not decrease with rest, swelling of the lower extremities that does not decrease, or increased pain, erythema, edema or drainage from the surgical incision. The Investigator should then determine if an evaluation is warranted.

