9.2 Adverse Event Reporting

Any AE that occurs during the subject's participation in the study will be recorded on the Adverse Event case report form. Pre-existing medical conditions or symptoms occurring prior to the initiation of the study will not be reported as AEs but a worsening of a pre-existing medical condition or symptom will be reported as an AE. Pain, neurological status and functional impairment should be considered AEs when a subject's complaint for any of these symptoms results in an unscheduled visit or when a subject presents with new or worsening symptoms as compared to a previous visit.

All AEs will be followed until the event is resolved or considered to be stable. Relevant source documentation must be available to confirm the occurrence of an AE and must be provided to the sponsor upon request.

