12.4 Analysis Populations

Analysis Populations are defined as follows:

- The Intent-to-Treat (ITT) population includes all enrolled subjects.
- The Per-Protocol population includes all enrolled subjects who have no major protocol violations (defined as not meeting inclusion/exclusion criteria or not being consented properly).

The effectiveness analysis will be performed on the ITT population. Analysis of the per-protocol population will be confirmatory of the ITT analysis. The safety analysis will be performed on the ITT population.

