12.6 Safety Analyses

Incidence rates of adverse events will be provided descriptively in tabular form for each study groups for the overall adverse event rate, serious adverse event rates, revision rates, removal rates, etc. at each follow-up interval.

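### Intra-operative exclusion ends study participation, so on the natural reading new adverse events after discharge have no collection route, although these subjects stay in the ITT safety population

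*Combined protocol and SAP*

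**What the plan says.** Section 8.3 sets the rule: "A Subject may be excluded from the study intra-operatively at the discretion of the Investigator if unexpected findings/occurrences" make it necessary to depart from the planned procedure. The justification "must be fully documented in the subject's medical record and on the Study Exit case report form". The one analytic consequence given is that "A subject who is excluded intra-operatively will be considered an overall treatment failure", which concerns effectiveness. Nothing is said about safety follow-up after the exclusion.

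On adverse events, Section 8.3 requires that "Intra-operative adverse events must be recorded and documented on an Adverse Event case report form", and it asks for events during the hospital stay to be recorded as well. Section 8.3.1 lists adverse event assessment from surgery to discharge. Section 9.2 makes recording on the Adverse Event form apply to events that occur while the subject is participating, and adds: "All AEs will be followed until the event is resolved or considered to be stable".

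On visits, Section 8.4 requires all subjects to return through 24 months and does not mention those excluded during surgery.

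On analysis, Section 8.1 counts a patient as enrolled from signed consent, Section 12.4 defines ITT as all enrolled subjects, and "The safety analysis will be performed on the ITT population". Section 12.6 states: "Incidence rates of adverse events will be provided descriptively in tabular form", broken down by follow-up interval. It does not say which subjects form the denominator at each interval.

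**The concern.** Adverse events are the primary safety objective (Section 5.2). The study has one arm and its safety analysis is descriptive, so the absolute rates are the whole safety result.

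The subjects affected are not a random subset. They are those whose operation departed from plan, selected by the surgeon's judgement. It is reasonable to expect some of them to be at higher risk of late infection, neurological events or further surgery, though the documents give no figure. Section 8.3 does not limit the exclusion to cases in which no Rail component was placed, so device exposure is possible. Section 9.1.3 makes the cause of any subsequent surgery a serious adverse event, and that is the kind of late event that would be missed. If it is missed, the late rates are too favourable by an amount that depends on how often surgeons use the exclusion.

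**Working it through.** **Step 1: what happens to an excluded subject's events.**

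| Event | Governing section | Covered? |
|---|---|---|
| During surgery | 8.3 | Yes |
| During the hospital stay | 8.3, 8.3.1 | Yes |
| Already open at exit | 9.2 | Yes, followed to resolution or stability |
| New, after discharge | 9.2 (participation) with 8.3 (exit) | No route on the natural reading; 8.4 points the other way |

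The reading in the last row rests on the Study Exit form. The protocol's other narrative uses of that form are loss to follow-up (Section 8.9) and withdrawal (Section 8.10), and both end participation. A subject excluded from the study on that form has, on the same footing, stopped participating, so the recording rule in Section 9.2 no longer reaches a new event. Section 8.4 read literally would still bring the subject back. The two cannot both apply, and sites may resolve the conflict differently.

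**Step 2: the plan's own N.** Section 12.3 gives 173 evaluable and 204 enrolled. A two-sided one-sample t-test with difference 4.0 − 2.2 = 1.8, SD 8.4 and alpha 0.05 has power 80.03% at N = 173, and 173/(1 − 0.15) = 203.5, so 204. Both figures reproduce. The point does not contest them; 204 serves only as the safety denominator below.

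**Step 3: illustrative size.** The documents give no exclusion rate and no event rate. Assumed: k = 4 or 10 excluded (about 2% or 5% of 204); post-discharge serious-event risk p = 5% in the other subjects and q = 5% to 30% in those excluded; none of the excluded subjects' post-discharge events recorded; all kept in the denominator.

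- True rate = [kq + (204 − k)p]/204
- Recorded rate = (204 − k)p/204
- Shortfall = kq/204

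| k | q | True | Recorded | Shortfall (points) |
|---|---|---|---|---|
| 4 | 5% | 10.2/204 = 5.0% | 10/204 = 4.9% | 0.2/204 = 0.1 |
| 4 | 20% | 10.8/204 = 5.3% | 10/204 = 4.9% | 0.8/204 = 0.4 |
| 10 | 30% | 12.7/204 = 6.2% | 9.7/204 = 4.8% | 3/204 = 1.5 |

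The last row is a relative understatement of 3/12.7 = 24%, and it needs a six-fold risk. A wider grid (k = 2 to 20, p = 5% to 20%, risk ratio 1 to 3) gives 0.05 to 5.9 points.

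**Step 4: if excluded subjects leave the denominator.** The recorded rate is then p = 5.0% and the shortfall is k(q − p)/204: zero at equal risk, 4 × 0.15/204 = 0.3 points in the second row, and 10 × 0.25/204 = 1.2 points in the third. Dilution disappears, but any higher-risk cases are still left out.

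**The case against.** The strongest reply is that nothing in the protocol says adverse event collection stops at an intra-operative exclusion. Section 5.2 promises continuous documentation of all adverse events, Section 8.4 recalls all subjects, and the in-hospital recording rule in Section 8.3 follows the exclusion rule with no exception. This stands in part: the stop is inferred from Sections 8.3 and 9.2. It does not remove the problem, because the general statements conflict with excluding the subject from the study on an exit form, and neither Section 5.2 nor Section 8.4 says how to treat an excluded subject.

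A reader might infer that every later event in these subjects is lost. The documents do not support that, since events up to discharge are recorded and open events are followed.

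A reader might also infer that the reported rates are necessarily diluted. ITT membership is explicit, but the interval denominator is undefined. The same gap affects withdrawn and lost subjects, for whom the plan allows about 15% (204 − 173 = 31), more than the 4 to 10 assumed here.

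Nor does the text establish that all these cases are complicated or had a partial Rail implantation. The rule covers unexpected findings as well as occurrences, applies only when they force a departure from the intended procedure, and must be justified in writing.

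Finally, the safety analysis is descriptive and no decision threshold depends on it. Where no Rail component remains, late events mainly describe the alternative procedure, and revision and removal in Section 9.1.3 are defined by the original implant. This limits the consequence for device-specific rates. It does not justify losing the events from a safety analysis defined on all enrolled subjects.

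**Conclusion.** The point holds in limited form. Sections 8.3 and 9.2 together leave new adverse events and subsequent surgeries after discharge without a clear collection route in subjects excluded during surgery, while Section 12.4 retains those subjects in the safety population and Section 8.4 points the other way. If the events are missed, the loss is selective and would tend to understate late serious-event and subsequent-surgery rates.

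The size cannot be set from the documents. The range of about 0.1 to 1.5 percentage points rests wholly on the assumed exclusion count and risks, on none of the excluded subjects' post-discharge events being captured, and on their staying in the denominator. A reader might take the 24% relative figure as the expected bias, but it is only the extreme corner of those assumptions. The effect may well be small. The change is worth making because it is cheap and concerns the primary safety objective.

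**What to change.** - In Section 8.3, replace exclusion from the study with discontinuation of the study procedure, the subject remaining in the study. Section 8.7 is a precedent: a subject who becomes pregnant stays in, with modified visits.
- Continue collection of adverse events, serious adverse events and subsequent surgeries on the existing visits and forms to 24 months, unless consent is withdrawn.
- Complete the Study Exit form only when participation actually ends.
- Show these subjects' events as a separate line in the safety tables, noting whether any Rail component was implanted, so that events after an alternative procedure can be told apart.
- Reconcile Sections 8.3, 8.4, 9.2, 12.4 and 12.6, and state the denominator used at each follow-up interval, including for withdrawn and lost subjects.

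The surgeon's discretion during the operation is unchanged. The cost is protocol wording and follow-up of what is likely to be a small number of subjects who have already consented. The downside is that adverse event rates may look slightly less favourable and will include events from an alternative procedure.
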